## 5.0 Study Intervention(s)/Interaction(s)

### 5.1 Description:

The intervention includes six primary focus areas:

(1). *PDE5-I drugs*: Participants will be offered the option to take 60mg sildenafil orally, 3x per week for 1 year. Participants for whom it is contraindicated, who are unwilling or unable to get a prescription from their physician, who prefer to use an alternative erection enhancer not covered by our study, or do not wish to take sildenafil will still be included in the intervention.

(2). *Pelvic floor exercises (a.k.a. Kegels)*: To strengthen the levator ani muscle, both to treat UI and climacturia, videos and educational materials will demonstrate proper technique for pelvic floor exercises. For climacturia, we will emphasize voiding bladder prior to sex, shaking of the penis; and clenching pelvic floor muscles during orgasm to keep sphincters closed.

(3). *Vacuum pump and (4) masturbatory exercises*: Participants will be given a penile vacuum pump and encouraged to use it with masturbation to stimulate blood flow to the penis. In addition, they receive three different sized dildoes to help with receptive anal sex and two penile constriction rings (aka “cock rings”).

(5). *A gay man’s/couple’s guide to sex after PCa treatment*: Our mobile-enabled interactive website will have videos modeling how GBM with PCa deal with sexual challenges (e.g., disclosing PCa to a sex partner); and a male couple discussing how they have good sex, post-treatment.

(6). *Social support*: We will provide participants with a coach to help them in rehabilitation, moderated forums and other opportunities for men to exchange advice and support with peers and experts.

Participants in the intervention group will receive the following:

- PDE5-I drugs. Participants will be given a letter and instructions to obtain a prescription from their doctor. They will then obtain their drugs online or over the phone via our pharmacy partner, Marley Drug. The study will pay directly for sildenafil for all intervention participants.
- A welcome package including a vacuum pump, tension bands and anal dilators (which are recommended tools in the content), and written educational materials (which are also provided in the online intervention).

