### 6.2 Study Procedures:

Following successful screening (see below), participants will review an online consent form which overview the study, study tasks, outlines risks and benefits, strategies to reduce risks, and risk-benefit analysis. After this, they participate in an initial telephone call from the project coordinator where they have the opportunity to ask any questions and have them answered, as well as verify information for cross-validation purposes. Then, if confirmed eligible and unique, they receive access to the baseline survey. Participants who complete the baseline survey will then be randomized, via a computer assignment, to a treatment or control group.

Participants in the control group will be notified by email. Thereafter, they will be contacted occasionally with survey links and reminders. As needed, additional casual communications will be used to increase retention.

Participants in the treatment group will be emailed immediately with a username and password to access the intervention. They will be mailed their welcome packet within one week.

Surveys will be conducted at baseline, and at 3, 6, 9, 12, 18, and 24 months follow-up. Surveys are attached.

Interaction for all participants in our study will include an online screening survey, a vetting phone conversation, an email confirmation, followed by an online baseline survey and five follow-up surveys. In addition, all participants can contact the study at any time using a 1-800 and/or our study email. In all email and phone contact, we will maintain HIPPA compliant standards to ensure no privacy violations. (e.g., we will not describe the nature of the study in phone or email messages). In addition, data will be maintained in password protected files on a secure server.

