### 6.3 Follow-Up:

Participants will be followed for twenty four months. Participants randomized to the intervention group will have access to the website and forums throughout the two years; however, it is anticipated that participants will experience the bulk of the intervention experiences during the first year. Sildenafil will only be provided for the first twelve

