**9.0 Study Duration**

**9.1 Describe:**

The duration anticipated for an individual participant's participation in the study. The total duration of participation is 24 months. Follow-up surveys will occur for both treatment and control groups at baseline, 3, 6, 12, 18, and 24 months. For participants in the treatment group, PDE5-I drugs will be provided for 12 months, but the online intervention will continue for 24 months.

The duration anticipated to enroll all study participants. We expect enrollment to last 13 months from January 2019 through February 2020. The duration anticipated to complete all study procedures and data analysis. The study will take five years total, including 15 months of preparation, 37 months of recruitment and intervention, and eight months for analysis.

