ID: SPH-2018-26507

NCT03343093

November 13, 2023

Title: Restore: Improving Sexual Outcomes of Gay and Bisexual Prostate Cancer Survivors

Statistical Analysis Plan

Data Analysis Plan (NCT03343093)

The purpose of Hypothesis 3.1 is to test whether structured rehabilitation (intervention) will yield statistically significantly better QoL, sexual and urinary outcomes than routine care (control) over 24 months. The data to be analyzed will comprise of 9 measurement occasions (1 baseline measurement, 7 quarterly measurements and 1 final measurement). The primary outcomes are: (1) sexual function measured by overall SF and EPIC sexual function and bother scores, and (2) urinary function measured by overall UI and EPIC urinary function and bother scores. We will use a mixed-effects model for repeated measures data to investigate the difference in the overall improvement trajectory between the intervention group vs. the control group over 24 months of the study on the primary outcome variables. If we find the statistical evidence to support our hypothesis, we will run an additional secondary analysis where we will compare different facets/components of the intervention. That is, we will investigate the main effects, along with the interaction effects among the different components of the intervention. To test for Hypothesis 3.2, we will incorporate treatment type, demographics, and health status as moderator variables into the statistical framework of mixed-effects models. We will evaluate Hypothesis 3.3 to test whether the effects of intervention are greater in newly treated men (<2 years since prostate cancer treatment) vs. men 2+ years, post-treatment. We will analyze this hypothesis by using the grouping variable (early vs. long term) in the mixed-effects model to study the difference in the improvement trajectory of the two levels of this grouping variable. To evaluate Hypothesis 3.4 we will assess if the overall slope coefficient for the men 2+ years post-treatment obtained from the mixed-effects model is statistically significant. The analysis of Hypothesis 3.5 would include the dependent variable of Climacturia, measured by single items from the GSFS scale, and the intervention components of pelvic floor exercises and PDE5-I drugs are the predictors/independent variables. We will test if pelvic floor exercises and PDE5-I drugs can predict improvement in Climacturia over time by using a mixed-effects model.

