Power Estimation. We expect 80% power to detect the statistically significantly differences between the intervention group and the control group. The power calculation was based on standardized effect size = 0.35, total number of observations per participant during the course of the study, $M = 9$, total number of participants, $N = 450$, assumed within-subject variability, $\sigma^2 = 0.50$, assumed between-subject variability, $\tau^2 = 0.20$ and a linear change over time.

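### The SAP plans no arm difference at month 12 or 24, and the single 24-month slope it appears to intend for Hypothesis 3.1 cannot show whether a year-1 benefit lasts

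*SAP*

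**What the plan says.** The SAP's Hypothesis 3.1 is that rehabilitation "will yield statistically significantly better QoL, sexual and urinary outcomes than routine care (control) over 24 months". The analysis is a mixed-effects model to "investigate the difference in the overall improvement trajectory between the intervention group vs. the control group over 24 months of the study". No coefficient, contrast, time point, alpha level or sidedness is given.

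Two places point to a linear slope. The Power Estimation paragraph ends its inputs with "and a linear change over time", and Hypothesis 3.4 asks whether the "overall slope coefficient for the men 2+ years post-treatment obtained from the mixed-effects model is statistically significant". Protocol section 17.3 (Data Analysis Plan) adds only that random coefficient models will be used, and leaves covariate adjustment optional. Section 6.1 stratifies randomisation by relationship status and time since treatment.

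On timing, Protocol section 6.3 anticipates that "participants will experience the bulk of the intervention experiences during the first year. Sildenafil will only be provided for the first twelve" months. Section 9.1 says "PDE5-I drugs will be provided for 12 months, but the online intervention will continue for 24 months". Section 5.1 makes the drug optional: men who "do not wish to take sildenafil will still be included in the intervention". Section 6.2 states: "Surveys will be conducted at baseline, and at 3, 6, 9, 12, 18, and 24 months follow-up". Section 9.1 omits month 9, and the SAP counts 9 occasions. Months 12 and 24 appear in all three schedules.

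**The concern.** The intervention is concentrated in the first half of follow-up, so a reader will want to know how large the arm difference is at month 12 and whether it is still there at month 24. A single straight-line slope compresses both answers into one number. Different histories can give the same slope, and a benefit that comes early or partly fades gives a small one. Differences read off the fitted line at months 12 and 24 are only one and two times the slope, so they add nothing.

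Because no visit contrast is planned, any month-12 or month-24 estimate in the report would have been chosen after the data were seen and would carry little weight. The unnamed coefficient adds to this: a linear slope, visit as a category, or a joint test would all fit the wording.

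**Working it through.** **Inputs from the documents.** N = 450, allocation 1:1, effect 0.35, within-subject variance σ² = 0.50, between-subject variance τ² = 0.20, linear change. Surveys at 0, 3, 6, 9, 12, 18 and 24 months (Protocol 6.2), or 9 quarterly occasions (SAP).

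**Assumptions, not in the documents.** Two-sided 5%; no dropout; time in years; τ² is the variance of individual slopes; 0.35 is in slope standard deviations; arm baselines are estimated freely.

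**1. The plan's own figure.** Planned slope difference = 0.35 × √0.20 = 0.157 per year. Sxx denotes the sum of (t − t̄)². For 9 quarterly occasions Sxx = 3.75, so the variance per participant is 0.20 + 0.50/3.75 = 0.333 and SE = √(4 × 0.333/450) = 0.0544. Then 0.157/0.0544 = 2.88 and power = Φ(2.88 − 1.96) = 82%. Time in quarters or months gives 95–96%, and a comparison of two means with SD 1 gives 96%. Of the readings tried, the yearly slope comes closest to 80%.

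**2. The same test with 7 surveys.** t̄ = 0.857 and Sxx = 2.982. Variance = 0.20 + 0.50/2.982 = 0.3677; SE = √(4 × 0.3677/450) = 0.0572. Power for 0.157 is 78%.

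**3. Slope fitted to different true histories.** If the true arm difference at time t is f(t), the expected slope is Σ(t − t̄)f(t)/Sxx, and power is Φ(slope/SE − 1.96) plus the small opposite tail. The benefit is set at 2 × 0.157 = 0.313, the planned month-24 difference.

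| True arm difference | Month 12 / 24 | Slope per year | Power |
|---|---|---|---|
| Linear to month 24 | 0.157 / 0.313 | 0.157 | 78% |
| Linear to month 12, then held | 0.313 / 0.313 | 0.159 | 80% |
| None to month 12, then linear | 0 / 0.313 | 0.154 | 77% |
| Reached by month 3, then held | 0.313 / 0.313 | 0.090 | 35% |
| Linear to month 12, half lost by 24 | 0.313 / 0.157 | 0.082 | 30% |
| Linear to month 12, all lost by 24 | 0.313 / 0 | 0.006 | 5% |

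For example, month 3 then held: 0.313 × 0.857/2.982 = 0.090; 0.090/0.0572 = 1.57; power 35%. The first three rows share almost one slope but have month-12 differences of 0.157, 0.313 and 0.

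**4. Sensitivity.** Half-loss power is 32% with 6 surveys and 30% with 9 occasions. With common arm baselines (assumed intercept variance 1.0 to 0.2) it is 39–60%, and month-3-then-held power is 53–85%. If τ² is a random-intercept variance, half-loss power is 57–96%, but that reading gives 98–100% for a linear effect and does not reproduce the stated 80%. If the month-12 benefit is only the planned 0.157, slope power is 29% if it holds and 11% if half is lost.

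**5. Precision of the added estimates, visit as a category.** The variance per participant of change from baseline is τ²t² + 2σ².
- Month 12: 0.20 + 1.00 = 1.20; SE = √(4 × 1.20/450) = 0.103; half-width 0.20.
- Month 24: 0.80 + 1.00 = 1.80; SE 0.126; half-width 0.25.
- Month 12 to 24: 0.20 + 1.00 = 1.20; SE 0.103; half-width 0.20.

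The month-12 interval excludes zero 86% of the time for a true 0.313 and 33% for 0.157. A loss of 0.157 between months 12 and 24 is also detected 33% of the time.

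**6. Why not a bend at month 12.** A two-piece line with a knot at month 12 is a little more precise (half-widths 0.18 and 0.22). But for a benefit of 0.313 reached by month 3 and fully held, it estimates 0.241 at month 12 and 0.174 at month 24. That is a false loss of 1 − 0.174/0.241 = 28%. Visit as a category returns 0.313 at both.

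**The case against.** Hypothesis 3.1 asks about outcomes over 24 months, and persistence after month 12 is not a stated objective. That stands, and it is why the added estimates should be secondary. The slope is also an inference: the trajectory wording fits visit as a category equally well, and the match to 80% depends on counting time in years. That stands too, and is a reason for the SAP to say which it means.

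Part of the power lost under fading is legitimate, since the month-24 difference really is smaller: at half loss, twice the slope is 0.164 against a true 0.157. This does not cover the early-and-held case, where the month-24 difference is 0.313 and twice the slope is 0.180. The 0.313 at month 12 is also twice the planned month-12 difference, so these histories are illustrations and not forecasts.

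A reader might infer that the benefit is expected to wane when sildenafil supply ends. The documents do not say so: the drug is optional and the online programme runs to month 24. A reader might also infer that the slope is the wrong primary test or that the trial is underpowered. Neither follows, because the stated power reproduces under the plan's own linear assumption. Nor is it safe to say that little is lost whenever the benefit holds: that is true for a linear rise to month 12 but not for early onset.

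**Conclusion.** The concern holds as a gap in pre-specification. The documents name no coefficient for Hypothesis 3.1 and plan no arm difference at any visit, and the slope they suggest cannot show whether a year-1 benefit lasts. With 7 surveys, a steady rise and a held month-12 benefit differ by 0.002 per year against an SE of 0.057. For an assumed benefit of 0.313, slope power falls from 78% under linearity to 35% with early onset and 30% with half loss. The power figures depend on how τ² and the baselines are read; the inability of one slope to separate these histories does not.

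The SAP is dated 13 November 2023. Planned enrolment to February 2020 plus 24 months ends in February 2022. A reader might infer from the date that the plan was written with results in hand. The documents do not show when unblinded data were first seen, so that cannot be concluded.

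**What to change.** State in the SAP that the primary test of Hypothesis 3.1, for each primary outcome, is the arm-by-linear-time slope over 24 months, with benefit as the stated direction.

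Add one secondary model per primary outcome with visit as a category and not a month-12 knot. Report the arm difference in change from baseline, with 95% CI, at months 12 and 24, and the month-12-to-24 change in that difference. Say that these describe persistence and do not replace the primary test.

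In Protocol section 17.3 (Data Analysis Plan), make inclusion of relationship status and time since treatment mandatory, since both are randomisation strata. The stratified analyses already planned there can stay.

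The cost is one extra model and three intervals per outcome, plus a few stratum parameters. The added model takes no power from the primary test. The intervals are wide (about ±0.20 at month 12, ±0.25 at month 24, ±0.20 for the change), so one that includes zero is not evidence of no benefit or of no fading. If the planned linear effect is true, the month-12 interval will include zero 67% of the time. Label the estimates post hoc unless they can be shown to predate access to unblinded data.

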## 12.0 Number of Participants

### 12.1 Number of Participants to be Consented:

We plan to recruit 450 participants: 150 participants who have undergone treatment in the past two years and 300 who have had at least two years since their PCa treatment.

We expect 80% power to detect the statistically significant differences between the intervention group and the control group. The power calculation was based on standardized effect size = 0.35, total number of observations per participant during the course of the study,  $M = 9$ , total number of participants,  $N = 450$ , assumed within-subject variability,  $\sigma^2 = 0.50$ , assumed between-subject variability,  $\tau^2 = 0.20$  and a linear change over time.

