## PROTOCOL TITLE: Restore: Gay Men and Prostate Cancer Aim III

All analyses will be completed in STATA version 12.0. Comparisons between the intervention and control groups and the outcome measures (EPIC Urinary, Hormone, Sexual, and Bowel, as well as FACT-P and BSI-18 scores) will be evaluated using random coefficient modeling. Stratified analyses will be conducted by time since treatment (2+ years vs <2 years) and relationship status. Models may be adjusted for treatment time, relationship status, comorbidities and demographic variables.

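### The SAP's tests for Hypotheses 3.3 and 3.4 name no intervention-versus-control contrast, so they cannot on their own support claims about the intervention's effect by time since treatment

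*SAP*

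**What the plan says.** The SAP's Data Analysis Plan takes its hypotheses in turn.

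- **Hypothesis 3.1** has its contrast written out: the mixed model is to examine the "difference in the overall improvement trajectory between the intervention group vs. the control group".
- **Hypothesis 3.2** brings treatment type, demographics and health status into the model as moderators.
- **Hypothesis 3.3** is to "test whether the effects of intervention are greater in newly treated men" than in men two or more years out. The analysis uses the early/long-term variable in the mixed model to "study the difference in the improvement trajectory of the two levels of this grouping variable".
- **Hypothesis 3.4** is not worded. The SAP says only that it will "assess if the overall slope coefficient for the men 2+ years post-treatment obtained from the mixed-effects model is statistically significant".

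The protocol's Data Analysis Plan (17.3) compares intervention with control by random coefficient models and then adds: "Stratified analyses will be conducted by time since treatment (2+ years vs <2 years) and relationship status". Neither document names an interaction between arm and time since treatment. The planned stratum sizes (Protocol 12.1) are "150 participants who have undergone treatment in the past two years and 300 who have had at least two years since their PCa treatment". The SAP's Power Estimation reads "We expect 80% power to detect the statistically significantly differences between the intervention group and the control group" and gives no power for any other hypothesis.

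**The concern.** Hypothesis 3.3 is a question of effect modification: is the gap between arms larger in one group of men than in the other? The contrast named for it is between the two groups of men. If the arms are pooled, each group's slope is its background change plus half of any intervention effect, because allocation is 1:1. Trends common to both groups cancel, but trends that differ do not. Men soon after treatment may well be on a different natural course from men years out, and the inclusion criteria (Protocol 10.1) also admit men whose treatment is still pending. Randomisation protects comparisons between arms. It does not protect a comparison of early with late men, or a single slope within one stratum.

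Studying both recently treated and longer-term survivors is one of the three advances claimed in Protocol section 1.0, and time since treatment is a randomisation stratum (Protocol 6.1). Statements that the program works better in newly treated men, or that it works in men 2+ years out, are therefore likely to be reported from these two tests. In the 2+ year men, the SAP's overall slope and the protocol's stratified arm comparison can give different answers.

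**Working it through.** **Inputs.** From the SAP's Power Estimation: N = 450, 9 occasions, σ² = 0.50, τ² = 0.20, standardized effect 0.35, linear change. From Protocol 12.1: 150 and 300 men. From Protocol 6.1: 1:1 allocation. The schedule in Protocol 6.2 (baseline, 3, 6, 9, 12, 18 and 24 months) gives 7 surveys, so results for 7 are shown in brackets.

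**Assumptions, because the documents do not state them.** Time in years, τ² taken as the variance of subject slopes, two-sided 0.05, no dropout. The planning effect on the slope is then d = 0.35 × √0.20 = 0.1565 per year.

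**Variance of one subject's estimated slope.** The sum of squared deviations of the occasion times is SS = 3.75 [2.982].

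var = 0.20 + 0.50/SS = 0.20 + 0.1333 = 0.3333 [0.20 + 0.1677 = 0.3677]

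**The plan's own figure.** SE of the difference between arms = √(4 × 0.3333/450) = 0.0544, giving power 0.82 [0.78]. This is close to the stated 80%, so the reading is workable.

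**The tests as written, with no intervention effect.** The background drifts are illustrative.

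- 3.3, arms pooled: SE = √(var × (1/150 + 1/300)) = 0.0577 [0.0606].
- 3.4, overall slope: SE = √(var/300) = 0.0333 [0.0350].

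| Drift per year | 3.3 rejects (difference between groups) | 3.4 rejects (drift in 2+ year men) |
|---|---|---|
| 0 | 0.05 | 0.05 |
| 0.05 | 0.139 [0.131] | 0.323 [0.298] |
| 0.10 | 0.410 [0.378] | 0.851 [0.815] |

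**The arm contrasts.**

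- 3.3, arm × time × group: SE = √(4 × var × (1/150 + 1/300)) = 0.1155 [0.1213]. Power is 0.273 [0.252] if the two effects differ by d. The difference detectable with 80% power is 2.80 × 0.1155 = 0.32 [0.34] per year, or 2.1 [2.2] times d.
- 3.4, arm × time in the 300 men: SE = √(4 × var/300) = 0.0667 [0.0700]. Power at d is 0.651 [0.609].

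**Masking.** The pooled tests see half the effect, d/2 = 0.078. A background trend of −0.078 per year brings the expected pooled contrast to zero. The 3.3 test then rejects 5% of the time against 27% [25%] for the three-way interaction, and the 3.4 test 5% against 65% [61%] for arm × time.

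**No power is lost by naming the arm.** Without background trend, the pooled tests see d/2 with half the standard error, so the ratio and the power are the same: 0.273 [0.252] and 0.651 [0.609].

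**Check by simulation** (10,000 trials, 9 occasions). The pooled 3.3 test rejected in 0.403 at a difference of 0.10, and the overall slope in 0.316 and 0.845 at drifts of 0.05 and 0.10. The arm contrasts stayed at 0.046–0.053 in these null cases. In the masking cases the rates were 0.048 against 0.277 (3.3) and 0.046 against 0.654 (3.4).

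**The case against.** The strongest reply is that 3.3 is loosely worded rather than wrong. Its aim is stated correctly, and the grouping variable is to be used in the mixed model, of which the only one specified so far is that of 3.1, with arm in it. No sentence says that arm is dropped. An interaction may well be intended. That is fair as to intention. But even with arm in the model, the only contrast named for 3.3 is between the two levels of the grouping variable. An analyst could report group × time and be following the SAP.

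A related reply is that the protocol's stratified sentence names no arm either, and is read as an arm comparison only from the sentence before it. That is so, and it is the natural reading. It does not rescue 3.3, because separate results by stratum do not test the difference between strata.

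On 3.4, the hypothesis is not stated, and if it asks only whether these men change over time, a slope test is right. This stands, so the criticism of 3.4 is conditional.

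The drifts are also chosen, not derived. A difference of 0.10 per year is about 64% of the planning effect (0.10/0.1565), and the masking cases use the one value that cancels the pooled contrast exactly. The scale is assumed too: changing only the time unit moves the main power between 0.49 and 0.95. The error rates therefore show the mechanism, not its likely size.

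**Conclusion.** The concern holds, as something that should be fixed. For 3.3, the named test does not match the stated hypothesis and cannot separate effect modification from differing background courses. For 3.4, the SAP gives a test without a hypothesis; that test cannot support an efficacy claim and differs from the protocol's stratified arm comparison. These conclusions rest on the text and do not depend on the numbers.

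The false-positive and masking rates depend on assumed drifts; with no drift, both tests keep their 5% level. The power figures for the arm contrasts do not depend on any drift, but they do rest on the time scale and reading of τ² that come close to the plan's 80%, and on no dropout. Hypothesis 3.1 is unaffected.

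**What to change.** - **Hypothesis 3.3.** Fit arm × time × time-since-treatment group with all lower-order terms. Name the three-way interaction as the test and report it with a confidence interval.
- **Hypothesis 3.4.** State the hypothesis. If it concerns the intervention's effect, test arm × time within the 2+ year stratum from the same model, report it with a confidence interval, and say that this is the stratified analysis in Protocol 17.3. If it concerns change over time only, say so and do not report it as an intervention effect.
- **Power.** State that the 80% covers only the main comparison of arms. Give the power of these two contrasts with its assumptions: about 61–65% for 3.4 at the planning effect, and about 25–27% for 3.3 if the effects differ by the full planning effect.

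The cost is a few lines of SAP text. The data and model family stay the same, and no power is lost against the pooled tests. The downside is that the stated power for two secondary hypotheses will look less favourable.

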## 4.0 Study Endpoints/Events/Outcomes

### 4.1 Primary Endpoint/Event/Outcome:

Health Related Quality of Life; measured as combined scores of the FACT-P and BSI-18 inventories

Sexual function and bother in anal and oral sex; measured via the EPIC-26 inventory and gay sexual functioning inventory

Urinary function and bother; measured via the EPIC-26

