### 4.2 Secondary Endpoint(s)/Event(s)/Outcome(s):

Self-reported climacturia, measured via the Gay Sexual Functioning Inventory, which we are developing for this study.

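### Climacturia, the only listed secondary outcome, has no explicitly stated comparison of the randomised arms; its one stated test uses two components that were not randomised separately.

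*SAP*

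**What the plan says.** Protocol section 4.2 has a single entry: "Self-reported climacturia, measured via the Gay Sexual Functioning Inventory, which we are developing for this study". The SAP describes it as "the dependent variable of Climacturia, measured by single items from the GSFS scale", without naming the items or their response scale. I take the inventory and the GSFS to be the same instrument.

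Arm comparisons are stated in two places. The SAP's Hypothesis 3.1 model looks at the difference in trajectory "between the intervention group vs. the control group over 24 months of the study on the primary outcome variables". It defines those variables as overall SF, overall UI and EPIC function and bother scores. Protocol section 17.3 (Data Analysis Plan) says that comparisons between the groups on the "outcome measures (EPIC Urinary, Hormone, Sexual, and Bowel, as well as FACT-P and BSI-18 scores) will be evaluated using random coefficient modeling". Neither names climacturia.

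The one analysis that does name it is Hypothesis 3.5: "We will test if pelvic floor exercises and PDE5-I drugs can predict improvement in Climacturia over time by using a mixed-effects model". The SAP also plans, if Hypothesis 3.1 is supported, a component analysis: "we will investigate the main effects, along with the interaction effects among the different components of the intervention".

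On design, Protocol section 6.1 randomises 1:1 to the online intervention or usual care. Section 5.1 makes sildenafil optional and keeps men who decline it in the intervention.

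**The concern.** Randomisation can answer one question about climacturia directly: does the package change it compared with usual care? Protocol section 2.0 presents the lack of treatment research on climacturia as a gap the trial will fill, so readers will look for that answer. The plan does not spell it out. It goes straight to which components predict improvement, a question the two-arm design was not built to answer. If components are coded by use, the men who exercise or obtain the drug have chosen to do so after randomisation, and they may differ from the others in how their symptoms would have changed anyway. The SAP's verb is predictive, not causal, but as the only stated result on the outcome it could be read as the trial's verdict on efficacy.

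**Working it through.** **1. The plan's own figure.** The stated 80% power is for intervention versus control. Inputs from the SAP (Power Estimation): effect 0.35, M = 9, N = 450, within-subject variance 0.50, between-subject variance 0.20, linear change. My assumptions: two-sided 5% test, effect standardised by the square root of 0.20, quarterly occasions with time in years, no dropout.
- Sum of squares of time = 3.75, so V = 0.50/3.75 = 0.1333.
- Noncentrality = 0.35 × √0.20 / √(4 × (0.20 + 0.1333)/450) = 0.1565/0.0544 = 2.876.
- Power = Φ(2.876 − 1.960) = 0.820, or 0.818 by the noncentral F distribution.

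This is close to the stated 80% under those assumptions; with time in unit steps it would be 0.953. Either way the figure describes an arm contrast. It says nothing about the Hypothesis 3.5 component test.

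**2. Where climacturia appears.**

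| Place | Comparison | Climacturia named? |
|---|---|---|
| SAP, Hypothesis 3.1 | Arm, primary outcomes | No |
| Protocol 17.3, Data Analysis Plan | Arm, listed scales | No |
| SAP, component analysis | Components, if 3.1 supported | No |
| SAP, Hypothesis 3.5 | Two components | Yes |

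**3. Hypothesis 3.5 coded by assignment.** Let A be arm and t be time. The model is

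y = b0 + b1·PFE + b2·PDE5 + b3·t + b4·PFE·t + b5·PDE5·t.

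Every man assigned the package is assigned both components, so PFE = PDE5 = A, and

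y = b0 + (b1 + b2)·A + b3·t + (b4 + b5)·A·t.

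Six columns have rank 4. Only the sums can be estimated, and b4 + b5 is the arm-by-time contrast. Adding a PFE × PDE5 term and its product with time gives eight columns, still rank 4, because A × A = A. This does not depend on the number of surveys.

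**4. Hypothesis 3.5 coded by use.** The columns can now be told apart, but only because men differ in what they chose to do. The contrast is between self-selected groups. Restricting to the intervention arm does not cure this. Treating controls as non-users is doubtful too: Protocol section 3.0 reports that most such men treat themselves informally. On adjustment, section 17.3 says models may be adjusted for treatment time, relationship status, comorbidities and demographics; treatment type is not in that list. The SAP brings in treatment type, demographics and health status as moderators for Hypothesis 3.2, but does not say so for 3.5.

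**5. How large could selection be?** The documents give no uptake and no link between use and prognosis, so any figure is illustrative. One simulation (2,000 trials per setting) used 450 men, the plan's variances, no true effect, about 50% uptake and a prognostic factor correlated 0.5 with slope. It compared users of one component with everyone else. With log-odds of use of 0, 0.5 and 1.0 per SD of that factor, the use test rejected in 4%, 19% and 50% of trials; the arm test rejected in 5.3%, 5.3% and 4.6%. Fitting both components jointly under other invented settings gave 6% to 65%. The direction is informative; the size is not a finding about this trial.

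**The case against.** The strongest reply is that the randomised comparison may already be there. If the Hypothesis 3.5 predictors mean assignment, the model collapses to arm-by-time for climacturia, as step 3 of the working shows. That stands. A reader might infer that no planned analysis uses randomisation for this outcome; with the coding unstated, the documents do not establish that.

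Second, the silence of the Protocol 17.3 list is weak evidence of exclusion. The list also omits the gay sexual functioning inventory, although section 4.1 makes it part of a primary outcome: "Sexual function and bother in anal and oral sex; measured via the EPIC-26 inventory and gay sexual functioning inventory". The list is therefore incomplete even for primary measures. In addition, the SAP's overall SF and overall UI scores are undefined, and climacturia might sit inside either. This also stands, but no passage says that it does, and a difference in an aggregate score would not test climacturia itself.

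Third, the means for a better use analysis exist: section 5.1 provides tools that track adherence, section 18.2 (Access to Participants) says PDE5-I use and prostate cancer treatment data are collected, and section 17.3 allows adjustment. These make an observational analysis workable. They do not make it randomised.

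**Conclusion.** The point holds in this form: no explicit arm comparison is stated for the sole secondary outcome, and its one stated test either cannot separate the components (rank 4 of 6) or is a non-randomised association. Which of the two applies depends on a coding the SAP does not give. I regard coding by use as likelier, because assignment coding would leave two predictors that are the same variable. The same limit applies to the conditional component analysis.

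The algebra needs no assumption beyond assignment coding. The size of any selection bias is not established, and the conclusion does not rest on the simulation. A reader might also infer that the main result is compromised; it is not, because Hypothesis 3.1 compares the randomised arms on the primary outcomes. This should be fixed, at the level of one secondary outcome and the component claims.

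**What to change.** **Add to the SAP.** As the test of the secondary outcome, state the intervention-versus-control by time contrast for climacturia in all randomised men, within the Hypothesis 3.1 mixed-effects framework. Name the GSFS item and its scoring, and use an ordinal or binary mixed model if the item is not continuous. Report the estimate with a confidence interval. State when the contrast was added relative to data review, and label it post hoc if after.

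**Reclassify.** Keep Hypothesis 3.5 and the component models as exploratory observational associations. Define use (source, threshold, time window, fixed or time-varying, which men) from the adherence tracking and the collected PDE5-I data. Adjust for treatment type and the section 17.3 covariates. Make no efficacy claim for a single component.

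**Cost.** Wording only, on data already planned, with three downsides.
- The trial no longer claims separate component effects.
- The contrast may be post hoc. Protocol section 9.1 plans enrolment to February 2020; adding 24 months gives February 2022. The SAP is dated November 2023, 21 months later, though the documents do not say whether that is when it was written or whether enrolment kept to plan.
- The contrast may be imprecise. If the 20% and 33.9% in section 2.0 applied to all 450 men, 450 × 0.20 = 90 to 450 × 0.339 ≈ 153 men would have climacturia. That is an assumption: the 20% describes otherwise continent men after radical prostatectomy, not this population.
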